Patients scheduled to have Aortic Valve Replacement (AVR), Coronary Artery Bypass Graft (CABG), or AVR/CABG combination procedure.. CABG may be single or multi-vessel, and may be done on-pump or off-pump
7. **Subject classification:** Check off all classifications of subjects that will be specifically recruited for enrollment in the research project. Will subjects who may require additional safeguards or other considerations be enrolled

Page 3 of 19

in the study? If so, identify the population of subjects requiring special safeguards and provide a justification for their involvement.

 Children	 Healthy	 Fetal material, placenta, or dead fetus
 Non-English Speaking	 Prisoners	 Economically disadvantaged persons
 Decisionally Impaired	 Employees	 Pregnant women and/or fetuses
 Yale Students	 Females of childbearing potential	

NOTE: Is this research proposal designed to enroll children who are wards of the state as potential subjects?

Yes No

8. **Inclusion/Exclusion Criteria:** What are the criteria used to determine subject inclusion or exclusion?

Inclusion criteria for consent process:

All elective AVR, CABG cases, on-pump or off-pump, or combination of AVR/CABG surgery in adult patients with preoperative LVEF \geq 45% subject to the following exclusions:

Exclusions during consent process:

1. Emergency/unplanned cases
2. EF $<$ 45% or moderate /severe RV dysfunction
3. Estimated GFR $<$ 30 mL/min
4. Patients on supplemental oxygen at baseline (home oxygen)
5. BMI $>$ 40 (calculated as the patient's weight in kilograms divided by the square of the patient's height in meters)
6. Patients with chronic opioid use preoperatively.
7. Patients with known neuromuscular disorders preoperatively.
8. Patients with a known sensitivity to Rocuronium or to Sugammadex.
9. Patients with known cognitive deficits preoperatively.
10. Patients $<$ 21 years of age

Exclusions after recruitment but prior to randomization:

1. Postoperative Bleeding (chest tube output $>$ 100cc/hr)
2. Treatment of anaphylactoid reaction intraoperatively.
3. Patient's temperature $<$ 35.5 or $>$ 38.3 degree Celsius at the time of ICU arrival.

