4. Determination that the patient will require prolonged mechanical ventilation possibly requiring muscle relaxation based on the intraoperative course and clinical judgment of the study PI or collaborating intensivists.
5. Intraoperative hypoxia or on arrival to the ICU. (Please see Study Flowchart).
6. Cardiac arrest
7. Sudden arrhythmia (Ventricular tachycardia runs/sudden bradycardia with improper pacemaker detection/function) precluding fast-track extubation protocol.
8. Need for two or more inotrope initiation precluding fast-track protocol. Only a single vasopressor/inotrope may be initiated without excluding the subject.
9. Postoperative ST changes.

10. A positive standard of care pregnancy test during your pre-operative evaluation

9. How will **eligibility** be determined, and by whom?

Eligibility at pre-op and post-op will be based on protocol specific inclusion and exclusion criteria and will be determined by the PI or Sub-I's in collaboration with the ICU attending physician

10. **Risks:** Describe the reasonably foreseeable risks, including risks to subject privacy, discomforts, or inconveniences associated with subjects participating in the research.

Sugammadex is generally safe and well tolerated. Potential risks associated with sugammadex are: hypersensitivity, including anaphylaxis/anaphylactic shock – previous trials suggest this risk is small. Cardiac arrhythmias including bradycardia & tachycardia where intervention is rare and responsive to usual treatment. Other reported risks include nausea, vomiting, constipation.

Bleeding was originally thought to be a side effect, but studies have since showed that Sugammadex falsely elevates the PTT without increasing bleeding risk. (see reference on last page.)

11. **Minimizing Risks:** Describe the way the above-mentioned risks will be minimized.

Patients will all be in a critical care environment and monitored very closely including: blood pressure, heart rate, and chest tube output will be tracked from arrival to the CTICU until extubation per ICU protocol. Subtle changes in the patient's hemodynamic status are easily seen and treated if necessary.

12. **Data and Safety Monitoring Plan:** Include an appropriate Data and Safety Monitoring Plan (DSMP) based on the investigator's risk assessment stated below. (Note: the HIC will make the final determination of the risk to subjects.)

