- e.) Unrelated: Adverse event is clearly not related to investigational procedures(s)/agent(s).

4. Plan for Grading Adverse Events:

The following scale will be used in grading the severity of adverse events noted during the study:

1. Mild adverse event
2. Moderate adverse event
3. Severe

5. Plan for Determining Seriousness of Adverse Events:

Serious Adverse Events:

In addition to grading the adverse event, the PI will determine whether the adverse event meets the criteria for a Serious Adverse Event (SAE). An adverse event is considered serious if it results in any of the following outcomes:

1. Death;
2. A life-threatening experience in-patient hospitalization or prolongation of existing hospitalization;
3. A persistent or significant disability or incapacity;
4. A congenital anomaly or birth defect; OR

5. Any other adverse event that, based upon appropriate medical judgment, may jeopardize the subject's health and may require medical or surgical intervention to prevent one of the other outcomes listed in this definition.

An adverse event may be graded as severe but still not meet the criteria for a Serious Adverse Event. Similarly, an adverse event may be graded as moderate but still meet the criteria for an SAE. It is important for the PI to consider the grade of the event as well as its "seriousness" when determining whether reporting to the IRB is necessary.

Only the following adverse events will be tracked. These AE's will trigger an immediate DSMB review; any incidence of anaphylaxis; unexplained hypotension requiring initiation of pressors; cardiac pacing within 5 minutes of drug administration; tachycardia, bradycardia or onset of atrial fibrillation; or increases in chest tube output considered clinically significant by the critical care team. The DSMB will be notified within 2 business days of determination by telephone or email. A written report will be provided within 7 days of the determination. Any incidents meeting SAE criteria will be reported per the IRB reporting policy.

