If a patient fails the 30 minute CPAP criteria, the ICU intensivist will be immediately notified. Every attempt will be made to correct the underlying cause of CPAP failure, and a prompt reassessment will be made as deemed appropriate by the intensivist to reattempt CPAP versus continuing controlled mechanical ventilation.

It is estimated conservatively that the study personnel will randomize 3 patients per week allowing for data collection to be completed within 1 year of study commencement. Data analysis and dissemination of findings will be conducted over the subsequent 6 months by the study institution investigators per the publication plan below.

Blinded analyses of the data will be performed by the study investigators along with the departmental statistician in the Department of Anesthesiology at the Yale School of Medicine.

**Variables/Time Points of Interest:** The primary outcome is the time to extubation, which will be the duration from arrival to the ICU to the extubation time. Participants' blood pressure, heart rate, and chest tube output will be tracked from arrival to the CTICU until extubation per ICU protocol.

**Statistical Methods:** Baseline comparability. We expect that the randomization process will produce reasonably comparable groups. However, the adequacy of the randomization will be assessed by comparing the distribution of baseline demographic and clinical characteristics among the intervention groups. Comparability for continuous variables will be examined graphically and by summary statistics (means, medians, quartiles, etc.). Categorical variables will be examined by calculating frequency distributions.

**Proposed statistical test/analysis:** Positively skewed variables will be log-transformed prior to hypothesis testing. For the primary outcome, a two-sided Student's t-test will be used to compare the time to extubation between the two groups. If necessary, covariate adjustment will be made using the multiple linear regression analysis method. Differences between means and 95% confidence intervals will be estimated to describe the magnitude of intervention difference between the two groups. As part of sensitivity analyses, the time-to-extubation outcome will be also analyzed by the Cox regression model. To compare the categorical adverse events between two groups, chi-square test or Fisher's exact test will be used.

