**Adverse Experience Reporting:** Throughout the duration of the study, researchers will adhere to good clinical practice and the guidelines of the institution. Patient vitals will be continuously monitored during and after the administration of the test drug. A data and safety monitoring board (DSMB) consisting of the head nurse and a senior critical care staff will meet monthly to discuss any serious events. Any incidence of anaphylaxis or unexplained hypotension requiring initiation of pressors or cardiac pacing within 5 minutes of drug administration will be reported and evaluated. Increases in chest tube output considered clinically significant by the critical care team will be noted. Any of these adverse events will trigger an analysis by the DSMB. If the DSMB determines that study drug may be causing an increase in adverse events, the study will be suspended until the DSMB is able to fully review the events and make a recommendation in consultation with the Yale Human Investigations Committee. The local Merck research

representative will also be notified about the events. If the data monitoring board and/or institutional review board (IRB) view that the study is unsafe, the study will be discontinued.

**Specific Safety Events to Be Reported During Manuscript Preparation:** For manuscript preparation, the rates of hypotension, anaphylaxis, and bleeding (i.e. Chest Tube output) will be reported and compared between active and placebo groups.

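### The bleeding comparison has no unit or common time window: the only defined event is a judged increase in chest tube output, although output is measured and its tracking stops at extubation

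*SAP*

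**What the plan says.** **Event and DSMB trigger.** SAP, Adverse Experience Reporting: "Increases in chest tube output considered clinically significant by the critical care team will be noted". The Protocol (Section I, 12, Data and Safety Monitoring Plan, item 5) lists "increases in chest tube output considered clinically significant by the critical care team" among the events that trigger immediate DSMB review. It opens that list with "Only the following adverse events will be tracked", so no other bleeding event is tracked. Neither document gives a volume, a rate, a period or a pre-dose reference for the increase.

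**Comparison.** SAP, Specific Safety Events to Be Reported During Manuscript Preparation: "the rates of hypotension, anaphylaxis, and bleeding (i.e. Chest Tube output) will be reported and compared between active and placebo groups".

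**Test.** The Proposed statistical test/analysis paragraph, the same in both documents, gives chi-square or Fisher's exact test for categorical adverse events. It names no analysis of chest tube output as a quantity.

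**Data available.** SAP, Variables/Time Points of Interest: "chest tube output will be tracked from arrival to the CTICU until extubation per ICU protocol". The Protocol says the same in Section I, 11. A number for bleeding, more than 100 cc/hr, appears only as an exclusion before randomization (Protocol Section I, 8).

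**Laboratory effect.** The Protocol (Section I, 10, Risks) states that "Sugammadex falsely elevates the PTT without increasing bleeding risk".

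**The concern.** Bleeding is one of three safety outcomes that the SAP undertakes to compare between arms, and a judged increase can lead through the DSMB to suspension of the study. Three features weaken the comparison.

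- **The outcome is undefined.** Two analysts could reasonably count judged events, patients above some rate, or total millilitres, and reach different answers.
- **Information is lost.** If the rate means judged events, a measured quantity is reduced to yes or no in a trial of 45 per arm. A real shift in drainage below the team's threshold would not be seen.
- **Follow-up depends on treatment.** The drug is meant to bring extubation forward, and extubation is where tracking stops. If the drug works, active patients have less time to accumulate volume or to have an event. The resulting bias makes the active arm look safer than it is.

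**Working it through.** **1. The plan's own figure.** Inputs from the power paragraph: difference 2 h, SD 2.89 h, two-sided alpha 0.05, power 90%. The exact two-sample t-test calculation gives 44.86, so 45 per group, with power 90.1% at 45. The stated size reproduces. It was set for time to extubation; no figure is given for bleeding.

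**2. What 45 per arm can show with a yes/no event.** The documents give no bleeding rate, so placebo rates of 5%, 10% and 15% are assumed. Normal approximation, with p the mean of the two rates:

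z = [(p1 − p0)√45 − 1.96√(2p(1 − p))] / √(p0(1 − p0) + p1(1 − p1))

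For 10% versus 35%: p = 0.225; z = (0.25 × 6.708 − 1.96 × 0.5906) / 0.5635 = (1.677 − 1.157) / 0.5635 = 0.92, so power is about 82%. Stepping p1 in whole percentage points, 35% is the first rate to reach 80%. The corresponding pairs are 5% versus 27% and 15% versus 42%. Fisher's test does worse: for 10% versus 30% the approximation gives 66.5% and exact enumeration of Fisher's test gives 57.5%.

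**3. What 45 per arm can show with a continuous measure.** The exact t-test calculation gives a detectable difference of 0.597 SD at 80% power. By normal approximation, (1.96 + 0.84) × √(2/45) = 0.59.

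**4. The two on one scale.** Assume that the judged event amounts to crossing a fixed cut on normally distributed output (after log transformation if needed). The shift that turns p0 into p1 is then z(1 − p0) − z(1 − p1):

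| Rates detectable with about 80% power | Implied shift | Continuous measure |
|---|---|---|
| 5% vs 27% | 1.645 − 0.613 = 1.03 SD | 0.60 SD |
| 10% vs 35% | 1.282 − 0.385 = 0.90 SD | 0.60 SD |
| 15% vs 42% | 1.036 − 0.202 = 0.83 SD | 0.60 SD |

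At the middle row the yes/no event costs the equivalent of (0.896/0.597)² = 2.25 times the sample size. Adjusting for the pre-dose rate would help the continuous measure further, by an amount that the documents do not allow one to compute.

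**5. Unequal observation time.** Planning mean 8.39 h; planned effect 2 h.

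- From ICU arrival: active 8.39 − 2 = 6.39 h; reduction 2/8.39 = 23.8%.
- From dosing the reduction is larger, because the pre-dose time is common to both arms. The documents give no dosing time. If dosing came 0.5, 1 or 1.5 h after arrival (assumed), it would be 2/7.89 = 25%, 2/7.39 = 27% or 2/6.89 = 29%.
- At a constant hourly rate, total volume or event counts would match between arms when the active hourly rate was 8.39/6.39 = 1.31 times that on placebo. An excess of about 31% per hour could therefore go unseen.
- With equal true hourly risk and 10% of placebo patients having an event over 8.39 h, the active arm would show 1 − 0.90^(6.39/8.39) = 7.7%, an apparent benefit with no real difference.

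Dividing by hours to extubation removes this only if drainage is constant over time. If it changes with time since surgery, the mean mL/hr to extubation is taken over different parts of that course in the two arms.

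**The case against.** **The compared rate may already mean measured output.** The comparison sentence glosses bleeding as chest tube output and omits the judgement wording, which strictly governs the tracked event and the DSMB trigger. The general rule on log-transforming skewed variables could also be taken to cover output. This stands in part: the documents do not tie the compared rate to the team's judgement. But the sentence speaks of rates, the only tests named for adverse events are categorical, and the only post-dose bleeding category defined is the judged one. If measured output is meant, its unit, window and analysis are still missing, and the extubation problem remains.

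**A reader might infer that the raised PTT biases the team toward calling bleeding on active.** The documents do not support that. Neither says that PTT is drawn between dosing and extubation or that it informs the judgement. What is judged is drainage. Nurses receive the drug blinded, and the clinical team is shielded from the neuromuscular readings and described as blinded to allocation. No masking of PTT is described, so the route is possible. Its direction is unknown, because staff who know that the elevation is false might call fewer events.

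**A reader might also want the 100 cc/hr limit as the event definition.** It is an eligibility limit, and nothing in the documents says that it suits a safety outcome. An event of ever exceeding it before extubation would also give placebo patients longer to qualify.

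**Conclusion.** The concern holds as a defect of outcome definition and follow-up. The bleeding comparison has no unit or window. The one defined event is a judgement that discards measured data. Observation ends at a point that treatment is designed to move.

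The size is about 0.83 to 1.03 SD detectable with a yes/no event against 0.60 SD with a continuous measure, and an active-arm observation period about 24% shorter, or more when counted from dosing. The first rests on assumed placebo rates of 5% to 15% and a threshold model for the judgement. The second rests on the full 2-hour effect and on the historical mean, which comes from isolated CABG patients after values above the 80th percentile were removed. A smaller effect would shorten the period less.

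A PTT-driven bias is not established and no size can be put on it. The primary outcome is unaffected.

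**What to change.** In the SAP paragraph on specific safety events for the manuscript:

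1. Make the main bleeding comparison the measured chest tube output in mL/hr, from charted volumes, over a stated post-dose window that is the same in both arms and does not end at extubation.
2. Estimate the between-arm difference with a 95% confidence interval by linear regression adjusted for the output rate from ICU arrival to dosing. Log-transform if skewed, and say how zero volumes are handled. Regression and log transformation are already in the plan for other variables.
3. Record the dosing time and the output up to dosing.
4. Report the team-judged events as a secondary count over the same window.
5. Leave the DSMB trigger on the team's judgement unchanged.

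The cost is some wording, a few derived variables, and abstraction of charted output for a short period after extubation in patients extubated early. The Protocol ends study participation at successful extubation (Section I, 4), so that sentence and the tracking period must be amended to allow it. The window must also lie within the time that output is still being charted, which the documents do not state and the sponsor would need to confirm. Clinical care does not change.

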- a. What is the investigator's assessment of the overall risk level for subjects participating in this study? Greater than minimal risk
- b. If children are involved, what is the investigator's assessment of the overall risk level for the children participating in this study? N/A
- c. Include an appropriate Data and Safety Monitoring Plan

1. Personnel responsible for the safety review and its frequency:

The principal investigator, with the DSMB will be responsible for monitoring the data, assuring protocol compliance, and conducting the safety reviews, which must be conducted at a minimum of every 3 months (including when reapproval of the protocol is sought). During the review process, the principal investigator (monitor) and the DSMB will evaluate whether the study should continue unchanged, require modification/amendment, or close to enrollment. Either the principal investigator, the IRB or DSMB have the authority to stop or suspend the study or require modifications.

2. The risks associated with the current study are deemed greater than minimal for the following reasons: (choose those that apply)

1. We do not view the risks associated with Sugammadex used as neuromuscular blocking reversal agent as minimal risk.
2. Given our experience with the administration of Sugammadex, an FDA approved medication, we do not view the proposed study as high risk.

Although we have assessed the proposed study as one of greater than minimal risk, the potential exists for anticipated and/or unanticipated adverse events, serious or otherwise, to occur since it is not possible to predict with certainty the absolute risk in any given individual or in advance of first-hand experience with the proposed study methods. Therefore, we provide a plan for monitoring the data and safety of the proposed study as follows:

3. Attribution of Adverse Events:

Adverse events will be monitored for each subject participating in the study and attributed to the study procedures / design by the principal investigator [name] according to the following categories:

- a.) Definite: Adverse event is clearly related to investigational procedures(s)/agent(s).
- b.) Probable: Adverse event is likely related to investigational procedures(s)/agent(s).
- c.) Possible: Adverse event may be related to investigational procedures(s)/agent(s).
- d.) Unlikely: Adverse event is likely not to be related to the investigational procedures(s)/agent(s).

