These UPIRSOs/SAEs will be reported to the IRB in accordance with IRB Policy 710, using the appropriate forms found on the website. All related events involving risk but not meeting the *prompt* reporting requirements described in IRB Policy 710 should be reported to the IRB in summary form at the time of continuing review. If appropriate, such summary may be a simple brief statement that events have occurred at the expected frequency and level of severity as previously documented. In lieu of a summary of external events, a current DSMB report can be submitted for research studies that are subject to oversight by a DSMB (or other monitoring entity that is monitoring the study on behalf of an industry sponsor).

7. Plan for reporting adverse events to co-investigators on the study, as appropriate the protocol's research monitor(s), e.g., industrial sponsor, Yale Cancer Center Data and Safety Monitoring Committee (DSMC), Protocol Review Committee (PRC), DSMBs, study sponsors, funding and regulatory agencies, and regulatory and decision-making bodies.

For the current study, the following individuals, funding, and/or regulatory agencies will be notified (choose those that apply):

- All Co-Investigators listed on the protocol.
- Study Grantor (Merck)
- Other Data Safety Monitoring Board (DSMB)
- Yale University IRB

The principal investigator [name] will conduct a review of all adverse events upon completion of every study subject. The principal investigator will evaluate the frequency and severity of the adverse events and determine if modifications to the protocol or consent form are required.

See also DSMB charter attached.

13. Statistical Considerations: Describe the statistical analyses that support the study design.

Variables/Time Points of Interest

The primary outcome is the time to extubation, which will be the duration from arrival to the ICU to the extubation time.

Proposed statistical test/analysis: Positively skewed variables will be log-transformed prior to hypothesis testing. For the primary outcome, a two-sided Student's t-test will be used to compare

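### The SAP's named safety comparisons and its DSMB triggers leave out tachycardia, bradycardia and new atrial fibrillation, which the protocol tracks and treats as triggers for board review

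*SAP*

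**What the plan says.** **Protocol.** Section I, item 12 (under the plan for determining seriousness) opens with "Only the following adverse events will be tracked", and makes every event on the list a trigger for immediate DSMB review. Besides anaphylaxis, unexplained hypotension that needs pressors, and pacing soon after the drug, the list contains "tachycardia, bradycardia or onset of atrial fibrillation; or increases in chest tube output considered clinically significant by the critical care team". It adds that "The DSMB will be notified within 2 business days of determination by telephone or email". Section I, item 10 gives among the risks of the study drug: "Cardiac arrhythmias including bradycardia & tachycardia where intervention is rare and responsive to usual treatment".

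**SAP.** Under Adverse Experience Reporting it says: "Any incidence of anaphylaxis or unexplained hypotension requiring initiation of pressors or cardiac pacing within 5 minutes of drug administration will be reported". It adds clinically significant increases in chest tube output and makes these events the ones that prompt a DSMB analysis. Under Specific Safety Events to Be Reported During Manuscript Preparation it states that "the rates of hypotension, anaphylaxis, and bleeding (i.e. Chest Tube output) will be reported and compared between active and placebo groups".

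**Both.** The statistical sections (protocol Section I, item 13; SAP, Proposed statistical test/analysis) give one general rule: categorical adverse events are compared between arms by a chi-square or Fisher's exact test. That rule names no events.

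**The concern.** Two documents for one trial each state a list of safety events, and the lists differ. The SAP's is the shorter, and what it lacks includes two risks that the protocol attributes to the study drug. The SAP also has heart rate followed until extubation (Variables/Time Points of Interest), yet its reporting sentence names no heart-rate event.

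Two things are at stake. A safety table built from the SAP's named events would have no row for tachycardia, bradycardia, atrial fibrillation or pacing. And the DSMB is given one set of triggers by the protocol and a smaller set by the SAP, with nothing in either document to say which governs.

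**Working it through.** **1. The lists side by side.** Rows follow protocol Section I, item 12; columns follow the two SAP paragraphs.

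| Protocol: tracked, and a DSMB trigger | SAP: DSMB trigger | SAP: named for comparison by arm |
|---|---|---|
| Anaphylaxis | yes | yes |
| Unexplained hypotension needing pressors | yes | yes, as hypotension |
| Pacing within 5 minutes of drug | yes (see below) | no |
| Tachycardia | no | no |
| Bradycardia | no | no |
| New atrial fibrillation | no | no |
| Clinically significant rise in chest tube output | yes | yes, as bleeding |

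The SAP's wording on pacing can be read as a separate event or as a treatment for hypotension. The three rhythm events are absent on either reading. The protocol list can be counted as seven event types or as five items separated by semicolons, so a percentage of omitted events would depend on the count, and none is given here. The SAP's Protocol Amendments section covers eligibility only and does not explain the difference.

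**2. Is the comparison by arm already specified?** The general test applies to categorical adverse events. Because the protocol tracks only the events on its list, the natural reading is that the test covers that list, rhythm events included. The gap is therefore in the named reporting list, not in the method.

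**3. Would the events still be reviewed?** Yes. The protocol requires safety reviews by the investigator with the DSMB, "which must be conducted at a minimum of every 3 months". The investigator also "will conduct a review of all adverse events upon completion of every study subject". The SAP has the board meet monthly on serious events.

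**4. What could the added rows show?** The plan's own figure comes first. For a difference of 2 hours, SD 2.89, two-sided alpha 0.05 and 90% power, the exact t calculation gives 44.86, so 45 per group, with power 0.901. The stated size reproduces and serves here only as the denominator.

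If all k events fall in one arm of 45, the two-sided Fisher p-value is 2 × C(45,k) / C(90,k):
- k = 5: 2 × 1,221,759 / 43,949,268 = 0.056
- k = 6: 2 × 8,145,060 / 622,614,630 = 0.026

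So 5 of 45 (11.1%) against none does not reach 0.05.

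For commoner events the documents give no rates. Assume control rates p₁ of 10%, 20% and 30%, an increase d (so p₂ = p₁ + d), and n = 45 per arm. With p̄ the mean of p₁ and p₂, power = Φ{[d − 1.96√(2p̄(1−p̄)/n)] / √([p₁(1−p₁)+p₂(1−p₂)]/n)}:
- d = 10 points: 0.262, 0.192, 0.166
- d = 20 points: 0.665, 0.545, 0.490

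The rows would describe the events. They could not rule out a difference.

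**The case against.** The strongest answer is that nothing is missing. The closed tracked list and the general test together already specify the comparison, the SAP's lists are not worded as exclusive, and a team that follows the protocol breaches nothing in the SAP. On the triggers, the protocol refers to an attached DSMB charter that is not in the text available here and may settle the matter. Bradycardia that leads to pacing within 5 minutes may also already reach the board under the SAP, if pacing is read there as a separate event.

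Most of this stands, and it is why the point is minor. It does not remove the mismatch. The general sentence names a test and no events, and the only place where the SAP names events for comparison leaves these out. Pacing captures only bradycardia that is paced within the window, whereas the protocol lists bradycardia without that condition.

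Two stronger readings are tempting. A reader might infer that rhythm events will go undetected or unanalysed. The documents do not support that: the events are tracked, reviewed and probably tested. A reader might also infer that the SAP's shorter list delays board review until the three-monthly meeting, and count the patients randomized meanwhile. That does not follow either. The three-monthly minimum belongs to the same protocol monitoring plan that requires notice within 2 business days, so one cannot be applied without the other.

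It is also fair to say that the protocol gives no threshold or time window for tachycardia or bradycardia. The new rows will be only as consistent as the recording of those events.

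**Conclusion.** The mismatch is plain on the page, but its effect is limited. The SAP's named safety report omits two risks that the protocol attributes to the drug, together with new atrial fibrillation and pacing. Its DSMB trigger list differs from the protocol's by the three rhythm events. The primary estimate, its test and the sample size do not change. This is an inexpensive alignment that could be made, not a flaw that threatens the trial.

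The conclusion assumes that both documents mean the same board, and that neither the DSMB charter nor the part of the SAP before its Study Protocol heading, which was not available, already aligns the lists. Confidence is high for the difference in wording and lower for any practical consequence.

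**What to change.** Extend the SAP's reporting sentence, keeping the events already there:

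*Every adverse event tracked under protocol Section I, item 12, including tachycardia, bradycardia, onset of atrial fibrillation and cardiac pacing, will be reported by arm as the number and percentage of patients and compared by the chi-square or Fisher's exact test already specified. With 45 patients per arm, a non-significant result must not be read as no difference.*

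This keeps the added events under the same test rule as the rest, so the statistical sections need no amendment.

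The two DSMB trigger lists (protocol Section I, item 12; SAP, Adverse Experience Reporting) must be reconciled with each other and with the charter. This review does not say which is right.

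The cost is a few more rows in the safety table and a text amendment. No extra patients are needed, and no new data collection, since the protocol already tracks these events. The drawback is low power, especially for rare events, which the added note makes explicit.
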